### **7.3 Advanced Therapy Investigational Medicinal Product definition**

The Drug Product (DP) can be classified as an Advanced Therapy Investigational Medicinal Product (ATIMP) belonging to the class of Cell Therapy Medicinal Products.

The following definitions shall apply throughout this study.

The Starting Materials is the Master Cell Bank (MCB) originated from cryopreserved non-immortalized human fetal neural precursor cells (hNPCs) BI-0194-008 cell line obtained from a single 10-12 weeks post-conception (wpc) human fetus and manufactured as defined in the Investigational Medicinal Product Dossier (IMPD).

The Drug Substance (DS) will consist of Working Cell Bank (WCB) obtained after expansion of MCB as defined in IMPD.

The DP will be constituted by thawed WCB-hNPCs re-suspended in their final formulation medium as defined in IMPD.

Medicinal product manufacturing and release will be performed at “Laboratorio di Terapia Cellulare e Genica Stefano Verri - ASST - Monza, Ospedale San Gerardo” (later also “Laboratorio Verri”), as described in the IMPD. Production will be performed according to GMP (Good Manufacturing Practice) certified facility authorized by Italian Ministry of Health according to D.L.vo 166/2003 for the production of sterile medicinal products, the production of specific me-

dicinal products obtained with particular technologies (i.e. cell therapy), and for primary packaging operations.

#### 7.4 Preparation of the drug product

When a new patient, enrolled in the clinical protocol, is ready for treatment, cryopreserved WCB vials will be thawed. Freezing medium will be discarded and cells re-suspended in 10 ml of injection medium and transferred to primary package(s).

#### 7.5 ATIMP packaging and labelling

The Medicinal Product will be labelled with a unique identification code of the patient and of the product, released by Laboratorio di Terapia Cellulare e Genica Stefano Verri, according to cGMP.

#### 7.6 ATIMP supply, storage and accountability

The ATIMP is produced at 37° C by “Laboratorio Verri” and it will be injected into patient's CSF at physiological body temperature. The DP will be shipped from “Laboratorio Verri” to OSR with a dedicated courier at controlled temperature (25°C ± 5°C) monitored with a data logger. The ATIMP will be released to an Investigator or another member of the investigating team designated by Sponsor or Principal Investigator. The person receiving the DP should control the data logger to check the temperature and report any non-compliance. Then the ATIMP will be transferred in a biohazard container at room temperature to the clinical ward for injection, according to OSR internal operating procedures.

Any non-compliance related to the delivery and / or transport of the drug will be managed according to OSR internal operating procedures.

The ATIMP will be kept at ambient or room-air temperatures (max 37°C) while waiting for patient's preparation for intrathecally injection.

The accounting of the ATIMP will be recorded in the ATIMP log in the Trial Master File (TMF). After injection the CRN will send to the OSR Pharmacy by fax the documentation certifying the receipt of the ATIMP, injection of ATIMP and waste disposal.

The PI is responsible for the accountability and traceability of the product.

#### 7.7 NIMPs packaging and labelling

NIMPs will be provided by the local pharmacy, according to institutional guidelines.

#### 7.8 NIMPs supply, storage and accountability

NIMPs will be delivered by courier to the responsible of pharmacy. The drugs has to be stored following the drug-specific SPC with access only to authorised personnel. The absolute amounts of drug administered per day and per patient have to be documented according to institutional guidelines.

The PI is responsible for supply, storage and accountability of the products.

#### 7.9 Further information, emergency procedures

No other special information is necessary.

#### 7.10 Methods of assigning patients to treatment groups

The protocol will consist of a total of four TC (from A to D), each of which receiving a single escalating dose of hNPCs injected intrathecally as it follows:

- TC-A:  $0.7 \times 10^6 \pm 10\%$  cells/kg of body weight;
- TC-B:  $1.4 \times 10^6 \pm 10\%$  cells/kg of body weight;
- TC-C:  $2.8 \times 10^6 \pm 10\%$  cells/kg of body weight;
- TC-D:  $5.7 \times 10^6 \pm 10\%$  cells/kg of body weight.

The trial will start with TC-A and will go through the subsequent enrolment of patients to be included in TCs from B to D.

Each cohort will consist of three patients at minimum. However in case of safety issue the numerosity of each TC will be increased to six patients, as explained below.

We define a DLT any adverse event of grade 3 possibly related to hNPCs or to the procedure. However we will not consider a DLT a prolonged hospitalization due to post lumbar puncture headache if not associated to any meningeal sign. We will not considered DLT adverse events related to concomitant treatments (tacrolimus and steroids)

After the inclusion of the first patient of the TC we will wait at least 14 days to treat the second patient. The same interval time will be used for all the further patients within the same TC. After the inclusion of all the planned patients within a TC, we will wait at least 3 months after the inclusion of the last patient before switching to the higher TC.

In case of none DLT within the TC, we will wait at least 3 months after the inclusion of the last patient and then we will move to the higher TC.

In case of 1 DLT within the TC, the cohort will be extended to 6 patients. If another DLT will be observed, the current dosage will be considered excessive and the immediate lower dosage will be considered MTD.

The safety monitoring board will review all safety data in the case of an AE  $\geq 3$  evaluated “possibly related to hNPC” by investigators and in any case before the shifts between TCs.

This will be repeated for every TC up to the end of the study.

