**5.5.2.1 Documentation of (serious) AE**

Between screening and last follow-up visit the patient will be asked and examined by the investigator for the occurrence of AEs. All AEs will be documented using CTCAE terms (see Appendix), including

- Severity (listed under)
- Onset date
- Stop date
- Causality assessment with study drug
- Action taken
- Outcome

The severity of AEs is defined as (see also CTCAE):

- Grade 1 mild
- Grade 2 moderate
- Grade 3 severe
- Grade 4 life-threatening
- Grade 5 death

All clearly related signs, symptoms and abnormal diagnostic procedures should be grouped together and recorded as a single term in the CRF.

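### The dose-limiting toxicity definition in section 7.10 counts only grade 3 events, so related life-threatening or fatal events do not enter the escalation and MTD rule as written

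*Combined protocol and SAP*

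**What the plan says.** Section 7.10 of the protocol contains the only definition of a DLT: "We define a DLT any adverse event of grade 3 possibly related to hNPCs or to the procedure". Two exclusions follow: a hospital stay prolonged by post-lumbar-puncture headache without meningeal signs, and events related to tacrolimus or steroids.

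The dose rule in the same section runs on the DLT count:

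- None: "In case of none DLT within the TC, we will wait at least 3 months" after the last patient is included, and the trial then goes to the next dose.
- One: "In case of 1 DLT within the TC, the cohort will be extended to 6 patients".
- A further one: "If another DLT will be observed, the current dosage will be considered excessive and the immediate lower dosage will be considered MTD".

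Patients within a cohort are staggered: "After the inclusion of the first patient of the TC we will wait at least 14 days to treat the second patient", and the same interval applies to those who follow.

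The section also provides for board review: "The safety monitoring board will review all safety data in the case of an AE" of grade 3 or above that is judged possibly related to hNPC "by investigators and in any case before the shifts between TCs".

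The severity scale in section 5.5.2.1 has five separate levels: grade 3 is severe, the next is "Grade 4 life-threatening", and grade 5 is death.

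**The concern.** The definition names a single grade where a threshold is needed. Followed to the letter, a severe event related to the cells has a fixed consequence for the dose, while a life-threatening or fatal one has none. The count is the only numerical rule for expansion, for declaring a dose excessive and for naming the MTD, so a reported MTD could rest on a tally that leaves out the worst events.

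This matters in this setting. Section 5.5.1 says that the safety profile of the cells is unknown and that they have never been used in MS. Section 5.5.2 says that any intraspinal injection may cause an inflammatory reaction whose severity cannot be predicted.

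A smaller gap lies beside it. The DLT definition covers events related to the cells or to the procedure, but the event-driven board trigger names only the cells. A severe event attributed to the procedure alone therefore reaches the board only at the review before the next cohort.

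**Working it through.** **Inputs.** DLT definition, dose rule, 14-day spacing and board trigger: section 7.10. Grades: section 5.5.2.1. Cohort size: 3 to 6, four cohorts (section 7.10 and synopsis). The stated maximum is reproduced: 4 × 6 = 24. The documents give no target DLT rate and no event rates, so the main check uses only the rule.

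**1. What the rule does with grade 4–5 events.** Place each patient in a cohort of 3 in one class: no event of grade 3 or above, a grade 3 event, or a grade 4–5 event, all related and not excluded. Each patient counts at most once. I take two or more DLTs among the first three to mean an excessive dose; section 7.10 implies this but does not spell it out. Six patterns include at least one grade 4–5 event:

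| None / grade 3 / grade 4–5 | Count as written | Count with grade ≥3 |
|---|---|---|
| 2 / 0 / 1 | 0, move up | 1, extend to 6 |
| 1 / 1 / 1 | 1, extend to 6 | 2, excessive |
| 1 / 0 / 2 | 0, move up | 2, excessive |
| 0 / 1 / 2 | 1, extend to 6 | 3, excessive |
| 0 / 0 / 3 | 0, move up | 3, excessive |
| 0 / 2 / 1 | 2, excessive | 3, excessive |

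The outcome changes in 5 of the 6. The patterns are not equally likely, so this is not a probability. The first row carries the point and does not need the inference about two or more DLTs.

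**2. Board trigger.** Let patient 1, treated on day 0, have an event attributed to the procedure alone.

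- Grade 3: this is a DLT, so the cohort extends to 6. At 14-day spacing, patients 2 to 6 can be treated on days 14, 28, 42, 56 and 70, up to 5 more patients before the pre-shift review if no second DLT occurs.
- Grade 4–5: as written, this is neither a DLT nor a trigger. Patients 2 and 3 can be treated on days 14 and 28, up to 2 more.

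**3. Illustration of how often the situation could arise (rates assumed).** With probability q per patient of a related grade 4–5 event, the chance of at least one among n patients is 1 − (1 − q)^n:

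| q | Cohort of 3 | Minimum 12 patients (4 × 3) |
|---|---|---|
| 1% | 0.03 | 0.11 |
| 5% | 0.14 | 0.46 |
| 10% | 0.27 | 0.72 |

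**4. Illustration of the effect on escalation (rates assumed).** With p the per-patient probability of an event that counts, P(move up) = (1 − p)³ + 3p(1 − p)² × (1 − p)³. Suppose half of the affected patients have only a grade 4–5 event, so that the literal rule sees p/2:

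| True rate, grade ≥3 | As written | Grade ≥3 |
|---|---|---|
| 10% | 0.973 | 0.906 |
| 20% | 0.906 | 0.709 |
| 33% | 0.783 | 0.434 |

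If a quarter have only a grade 4–5 event, the as-written figures are 0.944, 0.814 and 0.605. If none do, the two readings coincide. If all do, the literal rule moves up with probability 1 at any rate.

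**The case against.** The strongest reply is that nobody would apply the rule this way. The count does not act on its own: the board must review all safety data before every shift, there is a 3-month wait, and section 3.5 makes escalation conditional on no side effects being recorded. Read as literally as section 7.10, that condition would block escalation after any related grade 4–5 event. Section 7.10 also says, ahead of the detailed rule, that cohorts grow to six when there is a safety issue. Serious events go to the ethics committee within 24 hours (Table 2), fatal or life-threatening SUSARs are reported within 7 days (section 5.5.7), and section 6.3.1.2 allows suspension.

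Much of this stands. A related grade 4–5 event would be seen, the trial could be stopped, and investigators would very probably treat it as dose-limiting. But none of these provisions puts the event into the count. Suspension is discretionary, the board review has no dose decision attached, and section 10.5 leaves the committee's operating rules as an unfilled placeholder.

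The assumed rates are also open to challenge. Section 5.5.1 reports no hNPC-related adverse events in 42 patients, by a different route, and section 5.5.2 puts the rare lumbar puncture complications below 1%. These figures point to the low end of the illustrations, and the conclusion does not depend on them.

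Finally, the board-trigger gap is narrow. The cells go in through the same needle, and under section 5.5.3.1 an event counts as possibly related when a causal link cannot be excluded. A procedure-only attribution should therefore be uncommon, and 5 further patients is a worst case.

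**Conclusion.** The point holds: the DLT threshold is wrong as written. It is almost certainly a drafting error and not a deliberate choice. The protocol uses a greater-or-equal threshold for board review in the same section, and counting severe events but not life-threatening or fatal ones makes no clinical sense. The two thresholds in section 7.10 serve different purposes, so they do not contradict each other, but the mismatch shows what was meant.

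The size follows from the rule: one related grade 4–5 event in a cohort of 3, with no grade 3 event, gives a count of 0 and escalation instead of a count of 1 and extension to 6. The wider result of 5 changed outcomes in 6 patterns assumes one count per patient and that two or more DLTs in the first three make the dose excessive. The probabilities are illustrations only. Because the safeguards make actual harm unlikely, this should be fixed but does not by itself undermine the design.

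**What to change.** Amend section 7.10 in two places.

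1. Define a DLT as any adverse event of CTCAE grade 3 or higher that is at least possibly related to hNPCs or to the procedure. Keep the headache exception and the exclusion for tacrolimus and steroid events.
2. Extend the event-driven board trigger to events possibly related to the procedure, so that its scope matches the DLT definition.

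The cost is a short amendment. A cohort may expand to 6 where it otherwise would not, and the board may meet slightly more often, both within the stated maximum of 24 patients.

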1: General Physical examination on Day 0 will be performed before hNPCs Injection and the day after before discharge. 2: Pulse rate, systolic and diastolic blood pressure, respiration rate and axillary temperature. 3: Vital signs (pulse rate, systolic and diastolic blood pressure, respiration rate and axillary temperature) will be obtained before hNPCs injection and then after 15', 60' and 3 hours after the end of injection. 4: Complete blood cell count; Extensive clinical laboratory evaluations: PCR, LDH, Total Protein, albumin, IgG, IgA, IgM, AST, ALT, GGT, ALP, Na+, K+, Ca++, urea, uric acid, alkaline phosphatase, Total Bilirubin, Direct Bilirubin, Glucose, creatinine, creatinine clearance, ferritin, Serum Iron, transferrin, transferrin saturation, PT, PTT, urin analysis. 5: complete blood cell count, blood chemistry and urin analysis: PCR, AST, ALT, GGT, Na+, K+, Ca++, Total Bilirubin, Direct Bilirubin, Glucose, creatinine, creatinine clearance, LDH, urin analysis; 6: Blood chemistry (note 5) will be performed at day -1 only if not performed within seven days. 7: infectivological panel at screening: HBs-Ag, HBs-Ab, HBe-Ag, HBe-IgG, HBe-IgM, HBV-DNA, HCV-Ab, HCV-RNA, HIV-Ab, VZV-IgG, VZV-IgM, HSV1-IgG, HSV1-IgM, EBV-IgG, EBV-IgM, EBV-DNA, CMV-IgG, CMV-IgM, CMV-DNA, Toxo-IgG, Toxo-IgM, HSV2-IgG, HSV2-IgM, Galactomannan detection, TPHA, Quantiferon. 8: infectivological panel during follow-up: CMVDNA, EBV-DNA Galactomannan detection. 9: explained in detail in the main test, overall 25 mLs heparinized blood+ 5 mLs serum. 10: tacrolimus: will be administered as explained in the text and monitored as explained in the specified chapter. 11: prophylactic treatment are explained in the specified chapter. 12: Oral prednisone (deltacortene) will be administered only from day -1 till week 4 as explained in the text. 13: CSF examination will be performed at the same time of hNPCs administration. 14: At week 12 we will perform a brain and total spinal cord MRI with gadolinium for safety reason heparinized blood+ 5 mLs serum. 15: The pregnancy test will be performed always by urine, except the control before inclusion that will be done by serum. Emo1 = Complete blood cell count

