#### a) SHORT TERM (0-24 hours)

- overall survival
- overall safety and tolerability measured by AE recording
- changes in neurological conditions not related to disease
- proportion of successful intrathecal administration procedure (feasibility)

Day 0 = hNPCs administration

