### 5.5.9 Pregnancy

Pregnant and lactating women will not be included in the study. Females must have a negative pregnancy test prior to be included in the study and will be required to use a reliable and effective form of birth control during the study. Male participants will also be required to prevent pregnancy in their partners. The birth control methods which may be considered effective are: abstinence, oral contraceptives either combined hormonal or progestogen alone, injectable progestogen, subcutaneous contraceptive implants of etonogestrel or levonorgestrel, estrogenic vaginal ring, percutaneous contraceptive patches, intrauterine device or system (IUD) that has a certified failure rate less than 1% per year, male partner sterilization only with the declaration that he is the sole partner, male condoms combined with a female diaphragm either with or without a vaginal spermicide.

The birth control methods which are considered unacceptable in clinical trials are: periodic abstinence (calendar, symptothermal, post-ovulation methods), withdrawal (coitus interruptus), spermicides only, and lactational amenorrhoea method (LAM). For information refer to guidelines

[http://www.hma.eu/fileadmin/dateien/Human\\_Medicines/01\\_About\\_HMA/Working\\_Groups/CTFG/2014\\_09\\_HMA\\_CTFG\\_Contraception.pdf](http://www.hma.eu/fileadmin/dateien/Human_Medicines/01_About_HMA/Working_Groups/CTFG/2014_09_HMA_CTFG_Contraception.pdf)

At every study visit the sexual activity of participants of reproductive age will be re-assessed. If a subject who was previously sexually inactive becomes sexually active, s/he will be counseled about the need to use a reliable and effective form of birth control. Female subjects of childbearing potential will also be required to undergo pregnancy tests at regular intervals, including and especially prior to hNPCs administration. Women who had a positive pregnancy test will not be treated with hNPCs.

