## 7 Treatment Plan

### 7.1 Experimental Treatment/Drug

The protocol will consist of a total of four treatment cohorts (TC), labeled from A to D, each of which receiving a single escalating dose of allogeneic hNPCs injected intrathecally, as it follows:

- TC-A:  $0.7 \times 10^6 \pm 10\%$  cells/kg of body weight;
- TC-B:  $1.4 \times 10^6 \pm 10\%$  cells/kg of body weight;
- TC-C:  $2.8 \times 10^6 \pm 10\%$  cells/kg of body weight;
- TC-D:  $5.7 \times 10^6 \pm 10\%$  cells/kg of body weight.

The intrathecal injection of hNPCs will be performed in a hospitalized setting.

The patients will be left in Trendelenburg position for about 30 minutes and monitored for at least 24 hours. All patients will receive normal saline solution (500 cc).

Body temperature, blood pressure, heart rate and oxygen saturation will be measured at baseline and after 15, 60, 180 minutes and then before discharge. Any toxicity will be treated at the discretion of the attending neurologist.

All patients will receive an i.v. dose of **methylprednisolone** (125 mg) immediately prior to lumbar puncture.

The injections of cells will be performed with lumbar puncture in lateral decubitus position removing about 10 cc of CSF that will be used for chemical-physical, infectivological analysis and OBs/ BBB analysis. 2 CSF ml will be stored for further research analysis. CSF will be replaced with the 10 cc of suspension solution containing hNPCs (at 2 ml/min injection rate). The injection of stem cell will be performed in about 5 minutes. In case of traumatic lumbar puncture with haematic CSF, the injection of hNPCs will not be performed. A second attempt will be performed after  $15 \pm 3$  days.

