#### Day -1

- Neurological examination comprehensive of EDSS scale
- Vital signs
- AEs, SAEs record
- Relapse Assessment
- Concomitant medication revision
- Haematological blood examination: complete blood cell count, blood chemistry: will be performed if not performed within seven days
- Prednisone (Deltacortene) administration (50 mg)

At the end of all these assessment, patients will be assigned to one of the four different cohort of treatment (A-D) (see chapter Methods of assigning patients to treatment groups).

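### Section 7.10 counts the 14-day stagger and the 3-month escalation wait from inclusion, not from the actual hNPC administration, and no section moves either clock after a repeated puncture

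*Combined protocol and SAP*

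**What the plan says.** Section 7.10 sets two minimum waits. Within a cohort: "After the inclusion of the first patient of the TC we will wait at least 14 days to treat the second patient". The same interval applies to later patients in that cohort. Between cohorts: "we will wait at least 3 months after the inclusion of the last patient before switching to the higher TC", repeated in the rule for a cohort without a DLT. Section 7.10 neither defines inclusion nor gives it a study day.

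The protocol does have a dosing anchor. Section 5.3 states "Day 0 = hNPCs administration", but section 7.10 does not use it.

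Elsewhere inclusion is a step before dosing:
- Note 15 to Table 1 says pregnancy is tested by urine "except the control before inclusion that will be done by serum". Section 8.3.2 lists that serum test under screening.
- Section 5.5.9 says "Females must have a negative pregnancy test prior to be included in the study", and treats testing before hNPC administration as a separate requirement.
- Section 8.3.2 assigns the inclusion number within the screening section.
- Section 8.3.3 assigns the patient to a cohort on day -1.

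Section 7.1 allows for a failed first puncture, with a delay of 15 ± 3 days: "In case of traumatic lumbar puncture with haematic CSF, the injection of hNPCs will not be performed. A second attempt will be performed after" that delay. It does not mention either wait.

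**The concern.** The stagger exists so that one patient's early course can inform the decision to inject the next. That only works if the interval runs from injection to injection. Here it runs from an event that can come before the injection, by a day or a week on schedule and by much longer if the first puncture is traumatic.

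The setting makes this worth getting right. Section 5.5.1 calls the safety profile of the cells unknown and says they have never been used in MS. It adds that the 42 earlier exposures were by surgical injection into brain or spinal cord, not by lumbar puncture. The 14-day rule is the only stated minimum spacing between patients in a cohort.

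**Working it through.** The plan gives no derived figure for either wait, so the check is day arithmetic.

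**Inputs**
- Stagger: 14 days (section 7.10).
- Escalation wait: 3 months (section 7.10), taken as 89 to 92 calendar days. This conversion is an assumption.
- L, the days from inclusion to the planned injection: 1 if inclusion is cohort assignment on day -1 (section 8.3.3); 7 if it is the end of screening, using day -7, the latest day in section 5.2; 0 if treatment was meant. Section 7.10 speaks of inclusion in a cohort, so day -1 is the better-supported of the two pre-dose readings.
- R, the delay after a traumatic puncture: 15 - 3 = 12 to 15 + 3 = 18 days (section 7.1).

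**Stagger: earliest next injection, in days after the previous patient's actual injection**

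Ordinary schedule: 14 - L. Repeated puncture with the inclusion date left unchanged: 14 - L - R. A negative result means that the next patient may be injected first.

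| Inclusion read as | L | Ordinary | Repeat, date unchanged |
|---|---|---|---|
| Treatment (actual injection) | 0 | 14 | 14, because the clock moves with the injection |
| Cohort assignment, day -1 | 1 | 14 - 1 = 13 | 14 - 1 - 12 = 1 to 14 - 1 - 18 = -5 |
| End of screening, day -7 | 7 | 14 - 7 = 7 | 14 - 7 - 12 = -5 to 14 - 7 - 18 = -11 |

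On the day -1 reading, if the next patient is treated on the first permitted day, the two injections are at most 5 days apart. The week-1 visit (day 7) of whoever was injected first is then not yet due. If day -1 is re-dated with the second attempt, the gap is again 14 - 1 = 13 days.

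**Escalation wait: days after the last patient's injection when the wait ends**
- Ordinary, day -1: 89 - 1 = 88 to 92 - 1 = 91. Ordinary, day -7: 89 - 7 = 82 to 92 - 7 = 85.
- Repeat, date unchanged, day -1: 89 - 1 - 18 = 70 to 92 - 1 - 12 = 79. Day -7: 89 - 7 - 18 = 64 to 92 - 7 - 12 = 73.

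The ordinary figures do not show a shortfall between doses. Section 7.10 ends this wait at switching cohort, not at treating a patient, and says the trial "will go through the subsequent enrolment of patients to be included in TCs from B to D". If switching means including the next cohort's first patient, that patient's injection comes L days later, L cancels, and the dose-to-dose interval is 89 to 92 days. After a repeat the same cancellation gives 89 - 18 = 71 to 92 - 12 = 80 days, so the delay R is still lost.

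**The case against.** The strongest reply is that the authors meant treatment. The stagger sentence ends with treating the second patient, and the escalation wait sits beside the DLT rule, which concerns events related to the cells or the procedure and so patients already injected. On that reading nothing is lost. This is plausible and cannot be excluded. It remains true that one sentence uses inclusion for its start and treatment for its end, and that other sections place inclusion before dosing.

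The second reply concerns the repeated puncture. Day 0 is administration, so after a traumatic puncture it has not yet happened, and day -1 has no date until it does. Re-dating would be natural and would leave a 1-day loss. This carries weight: the 1-to-minus-5-day result needs an inclusion date that stays fixed. But no section says that cohort assignment is repeated or re-dated, and an inclusion recorded at screening would not move by itself.

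Third, both waits are minimums, the trial has a single centre, and the investigators would know that the previous patient had not been injected. There is also inpatient observation (section 7.1), board review after related events of grade 3 or above and before each cohort shift (section 7.10), and the power to suspend the study (section 6.3.1.2). These reduce the risk, but none sets a minimum interval between injections.

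A reader might also infer that escalation would come too early because it could precede the week-12 safety MRI (day 84). The documents do not support that as a breach: no stated rule ties escalation to that scan.

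**Conclusion.** The point holds as a wrong or ambiguous start point for two safety intervals. Its weight is minor to moderate, and it is best described as a cheap improvement.

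On the ordinary schedule the guaranteed spacing within a cohort is 13 days on the better-supported pre-dose reading, 7 on the weaker one, and 14 if treatment was meant. The material gap is the missing rule after a traumatic puncture. It requires a repeated puncture, an inclusion date that is not re-dated, and a next step taken on the first permitted day. The shortened escalation wait further requires that the repeat delays the last injection in a cohort. The documents do not say how often punctures are repeated, so the chance of this sequence cannot be estimated.

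Two stronger readings should not be drawn. The documents do not show that the stagger fails in normal running, nor that patients are expected to be injected out of order. Nor do they show that the ordinary 3-month wait is short, since the lead time may cancel.

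**What to change.** In section 7.10, replace inclusion with actual hNPC administration as the start of both waits, including the repeat of the 3-month rule. Add that after a repeated puncture the clock runs from the successful injection. The word actual matters: counting from the planned puncture date would still allow 14 - 12 = 2 to 14 - 18 = -4 days.

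No patients or procedures are added. Each wait becomes 1 day longer (day -1 reading) or up to 7 days longer (day -7 reading). After a repeated puncture the affected wait is 1 + 12 = 13 to 1 + 18 = 19 days longer, or 7 + 12 = 19 to 7 + 18 = 25 on the day -7 reading, if the date would not otherwise have been re-dated.

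Without repeats, four cohorts of three have 4 × 2 + 3 = 11 waits, so the shortest schedule grows by at most 11 days (11 × 7 = 77 on the day -7 reading). At the maximum of 4 × 6 = 24 patients there are 4 × 5 + 3 = 23 waits, adding at most 23 days (23 × 7 = 161). If treatment was always meant, the change costs nothing and removes the ambiguity.
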